## **10. Subjects - Risk and Benefits**

### **Risks to Subjects**

The clinical intervention is intended to improve outcomes for subjects, including symptoms, quality of life, caregiver burden, depression, satisfaction, and self-efficacy. In particular, the intervention seeks to align healthcare received by patients with their preferences. However, there are some risks associated with participation, outlined below.

#### **1. Medications (patient subjects only)**

There are risks to patients related to the prescription of medications, particularly those that may be prescribed for pain (including opioids) and behavioral and psychiatric symptoms (antipsychotics). These medications will only be prescribed in accordance with clinical guidance, after careful consideration of the risks and benefits of their use. In particular, we will only use antipsychotics for the management of behavioral symptoms where reversible causes have been considered and treated as appropriate, and the patient is at extreme risk or in severe distress. In all cases where a new medication is commenced we will inform the patient's treating physician and counsel the caregiver about the medication.

Please note that we are enrolling patients with advanced dementia who are by definition at high risk of both worsening delirium and function, hospitalization, death and other serious events. As such these outcomes are expected and will not be considered SAEs.

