### **Safeguards to protect Subjects rights and welfare**

We have undertaken numerous steps to protect patients' rights and safeguard their welfare, in light of their likely impaired capacity.

1. The patient's healthcare provider will introduce the study and determine interest before we approach the patient and caregiver.
2. We will ask the patient's healthcare provider to complete a capacity assessment. Where the patient lacks capacity to consent to study involvement (which we anticipate in most cases) we will follow standard protocol for consent in patients lacking capacity (i.e., their LAR will provide authorization)
3. We will clearly state the dyad's right to refuse participation and to withdraw at any time during the study period without affecting their routine clinical care.
4. The intervention will be provided by a team of highly trained professionals, who have extensive experience in caring for patients with moderate-severe dementia and their caregivers.
5. The procedures undertaken in the patient's home (which may include: clinical examination, recording of vital observations, blood draws, X rays, ultrasound) will be dictated only by the clinical needs identified using standardized assessments. The clinical team will record all encounters with the patient or caregiver in the secure

electronic medical record. Note - as of 3/19/2020 we will no longer be doing home visits as part of the intervention due to the risk of transmission of COVID-19 to a high risk population, with the exception of clinical emergencies that cannot be managed using telemedicine as previously documented.

6. Medications will be prescribed and de-prescribed according to need to treat clinical problems on the basis of clinicians' experience and in accordance with relevant guidelines. In all cases, medications will be prescribed by licensed providers, either the palliative care MD or the palliative care advanced practice nurse. Risks and benefits will be discussed in all cases of prescribing or de-prescribing a medication with the patient where they have capacity, or with their LAR when the patient lacks capacity. Additionally, the provider will communicate all medication changes to the patient's nominated physician.

7. All appropriate measures will be taken to ensure the secure transmission, storage and use of protected health information.

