### **Provisions for Research Related Harm / Injury**

It is not anticipated that patients or caregivers will come to harm during this study, as the intervention does not differ substantially from routine clinical care that is based on clinical guidelines. The clinical team has vast experience and competence in managing side effects and adverse events related to medication use in these patients. Where adverse events related to medication use cannot be managed in the home, the patients will be admitted to hospital at Mount Sinai. Generally, this medical care will

be billed to the research subject and/or his/her health care insurance in the ordinary manner and the research subject will be responsible for all treatment costs not covered by insurance, including deductibles, co-payments and coinsurance. This does not prevent the research subject from seeking payment for injury related to malpractice or negligence. As outlined above, interviews can arouse emotions in patients and caregivers. We have outlined the provisions for this eventuality above.

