**Principal Monitor**

**Additional Monitors**

### **Specific Items That Will Be Monitored for Safety**

All SAEs, regardless of treatment group or relationship to research, will be reported to the IRB within 24 hours in a full written report. Note that these patients have advanced illness and are receiving palliative care. As such deaths will be recorded and regularly reported to the IRB but deaths are not in and of themselves considered SAEs due to the nature of the patient population. We will review each death and evaluate the relationship of that death to any medications prescribed or recommended by the study team. If the team believes there is a causal relationship between the prescription of the medication and the subject's death, this will be reported to the IRB as a serious adverse event.

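### The protocol's sections disagree on which serious events count as SAEs, and read literally a non-fatal serious harm from a study-team prescription has no stated expedited reporting route

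*Protocol*

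**What the plan says.** Three parts of the protocol decide how a serious event is classed and reported.

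- **Section 10, Risks to Subjects, item 1 (Medications).** After naming opioids and antipsychotics as medication risks, it describes patients as "by definition at high risk of both worsening delirium and function, hospitalization, death and other serious events" and concludes: "As such these outcomes are expected and will not be considered SAEs". No exception by cause is given.
- **Section 24, Specific Items That Will Be Monitored for Safety.** The general rule is "All SAEs, regardless of treatment group or relationship to research, will be reported to the IRB within 24 hours", in a full written report. Only one kind of event is taken out: "deaths are not in and of themselves considered SAEs due to the nature of the patient population". For every death, the team is to "evaluate the relationship of that death to any medications prescribed or recommended by the study team". Where the team finds such a link, the stated consequence reads: "causal relationship between the prescription of the medication and the subject's death, this will be reported to the IRB as a serious adverse event". No such review or consequence is stated for a non-fatal event.
- **Section 24, Frequency of Data Review.** Adverse events that are serious and also unexpected go to the IRB, the NIA program officer and the independent monitor within 48 hours. All adverse events follow IRB policy. There is a quarterly report to the monitor and a 6-monthly report to the NIA program officer. In the first month the investigator's side and the monitor check together which events are study related.

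Two other places show that the case is foreseen. In section 8 (Safeguards), "medications will be prescribed by licensed providers, either the palliative care MD or the palliative care advanced practice nurse". In section 10 (Provisions for Research Related Harm / Injury), "Where adverse events related to medication use cannot be managed in the home, the patients will be admitted to hospital at Mount Sinai".

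**The concern.** Prescribing by the study team is part of the intervention, and control patients do not receive it. A serious drug reaction is therefore among the harms most directly attributable to what is being tested. Section 10 removes from SAE status the form such a reaction is likely to take, an admission or a worsening of delirium, and does so under the medication-risk heading. Section 24 recognizes that an expected outcome can still be caused by a study-team drug, but acts on this for deaths only.

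At stake is prompt notice of a drug-related harm to the IRB, the funder's program officer and the monitor. There is also a cost in the other direction. If section 24 is followed on its own, every admission counted as serious needs a full written report in 24 hours, including admissions unrelated to the study, in a population that the protocol expects to be admitted. Staff cannot tell from the protocol which rule to apply.

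**Working it through.** No arithmetic applies. The check is to take four events through the three sections and see whether the answers agree. One assumption is needed: that a hospital admission counts as serious. The protocol does not define the term. Section 24 (Grading System to Evaluate Adverse Events) names three categories of event and defines neither serious nor expected. The list in section 10 does, however, group hospitalization and death with other serious events.

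| Event | Section 10, Medications, read literally | Section 24, Specific Items, read alone | Section 24, Frequency of Data Review: 48-hour notice |
|---|---|---|---|
| Death judged caused by study-team medication | Not an SAE | SAE, reported to the IRB | Not triggered if death is expected |
| Death with no such link | Not an SAE | Not an SAE; recorded and regularly reported | Not triggered |
| Admission caused by a study-team prescription | Not an SAE | SAE, IRB within 24 hours | Not triggered if admission is expected |
| Admission unrelated to the study | Not an SAE | SAE, IRB within 24 hours | Not triggered if admission is expected |

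1. **Row 2 is consistent. Rows 1, 3 and 4 are not.** In each of these three, section 10 and section 24 give opposite classes to the same event.

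2. **Row 3 is where notice can be lost.** If section 10 decides what an SAE is, the 24-hour rule has nothing to act on, because it covers SAEs only. The 48-hour rule fails as well, because section 10 has labelled the event expected. Section 24 provides a way back to SAE status for a death judged causal, and none for this admission.

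3. **What remains for row 3.** It is still an adverse event. It goes through IRB policy, for which the documents give no time limit, and into the quarterly and 6-monthly reports. The joint check of relatedness is promised for the first month only.

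4. **Row 1 is also incomplete.** For a death judged causal, section 24 (Specific Items) names the IRB alone. Notice to the NIA program officer and the monitor within 48 hours depends on the death being unexpected, and section 10 calls death expected.

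5. **The open category widens the conflict.** Section 10 ends its list with further serious events, unspecified. Taken literally, this leaves very little for the rule on all SAEs to cover.

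6. **The IRB clocks differ.** Specific Items gives the IRB 24 hours for every SAE. Frequency of Data Review gives it 48 hours for those that are also unexpected. A report at 24 hours meets both, so this is a mismatch and not an impossibility, but the protocol should not state two limits for one event and one recipient.

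**The case against.** The strongest reply is that section 10 speaks only of the natural course of dementia. Its reason is the disease: patients with advanced dementia are at high risk, and the outcomes are expected for that reason. A reaction to a prescribed drug is not expected because someone has dementia. The wording on deaths in section 24 points the same way. On this reading the 24-hour rule applies to a drug-related admission, and the 48-hour rule can apply too. This is plausible and may well be the intent. But section 10 does not say it, the sentence stands under medication risk, and section 24 found it necessary to write out a causal exception for deaths. The reading also leaves row 4 of the table unresolved.

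A second reply is that a separate data and safety monitoring plan is listed in sections 24 and 26, and that IRB policy governs all adverse events. Either may define seriousness, expectedness and timing. That stands as a limit on this point: neither was available. It would not remove the contradiction within the protocol.

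A reader might go further and infer that drug harms would go unreported or unmonitored. The documents do not support that. Reporting under IRB policy and the quarterly and 6-monthly reports continue, charts are abstracted after every hospitalization (section 12, source records), and admissions are a study outcome. Nor do they support a claim of a particular delay, since the IRB-policy route has no stated time and might be fast.

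**Conclusion.** The contradiction is real and should be corrected. Section 10 removes a broad and open-ended set of serious outcomes from SAE status without regard to cause. Section 24 removes deaths only, restores those judged caused by study-team medication, and otherwise applies the 24-hour rule regardless of relationship. Followed literally, section 10 leaves a non-fatal serious harm from a study-team prescription with no stated expedited route.

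The size can be stated only in kind: which events change class and which notices fall away. The documents give no rates of admission, delirium or drug reaction, so no number of affected events is claimed. Counting outcome types in the section 10 list would add nothing, since one of them is open-ended. It would also be wrong to infer a bias in the trial's results. The SAP plans no adverse event comparison, and its counts of hospital admissions and days (SAP section 4) do not depend on SAE status.

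The conclusion assumes that an admission is serious and that the protocol is read without the monitoring plan. Confidence is medium, because the disease-only reading may be what was meant.

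**What to change.** Reconcile section 10 (Medications) and the two parts of section 24 with each other and with the monitoring plan:

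1. In section 10, limit the exclusion to events judged due to the underlying illness and not related to the study intervention. Relatedness should cover prescribing, de-prescribing and the other components, such as telemedicine support and paramedic visits. A test tied to medication alone would release events caused by the rest of the intervention.
2. In section 24 (Specific Items), extend the relatedness review and its SAE consequence from deaths to hospitalizations and other non-fatal serious events, so that both sections exclude the same events.
3. In section 24 (Frequency of Data Review), state that an event judged related to the intervention is not treated as expected. Use the same relatedness term in all three places.
4. State one consistent reporting clock for the IRB.

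The cost is wording in three places. Chart abstraction after every hospitalization already supplies the data on admissions; other non-fatal events rest on what the clinical team already records. The downside is more relatedness determinations and some more expedited reports, probably few, though the documents give no rates. These determinations can reveal the arm, so they must be kept from the research coordinator who conducts the blinded follow-up interviews (section 12, study design).

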#### **2. Breach of confidentiality (patients and caregiver subjects)**

Information about any encounter with a patient or caregiver by the clinical team during the course of the study will be recorded in the electronic medical record (EPIC), a HIPAA secure platform used for storage and transmission of healthcare information across the clinical network. Any video visits that are used in the course of clinical care will use software compliant with Office for Civil Rights framework. While there is a theoretical risk of breach of confidentiality, this is no more than would be encountered in routine clinical care. There is a theoretical risk of loss of protected health information for subjects in both intervention and control arm that is recorded for the purpose of research. However, this risk is minimized through precautions detailed in the "Data" section of this proposal.

#### **3. Risks of interviews**

Talking about illness may arouse difficult emotions in patients, their proxies, and caregivers. However, research coordinators are trained to recognize these emotions, and to respond with sensitivity. Where subjects show signs of significant distress, the research coordinator will discuss the case with the Principal Investigator, who will decide on whether it is necessary to inform the subject's healthcare team. This course of action will only be taken with the subject's consent, unless there is significant risk of harm to the subjects or others, in which case consent to share the information arising from the interview is not a requirement (but should be sought).

### **Description of Procedures Taken to Lessen the Probability or Magnitude of Risks**

Patients in the intervention arm will be cared for by a highly trained team of providers, with experience in caring for patients with dementia and their caregivers. Our intention is to have written communication with the PCP at the time the patient comes on to the program to establish roles within this co-management model of care. As part of this communication, we would include the statement: "Where there is a need to prescribe medications, we will seek your agreement prior to prescribing. However, if we do not receive a response within 48 hours, or the clinical situation demands a more urgent response, we will not await your agreement before prescribing medications. In all cases, we will inform you of our action." This written statement is also included in the Attachments tab.

The research team are highly experienced and all research coordinators will be trained on sensitive interviewing and research protocols.

Any expression of significant mental health issues exposed in a survey response will be discussed with the PI or study manager. We will set thresholds for escalation to the PI based on scores on Zarit Burden Inventory and PHQ-9, any expressions of distress, and any concerns by the study team. The PI or study manager would then contact the caregiver to encourage them to seek additional support from their primary physician and/or the intervention team as appropriate.

### **Provisions for Research Related Harm / Injury**

It is not anticipated that patients or caregivers will come to harm during this study, as the intervention does not differ substantially from routine clinical care that is based on clinical guidelines. The clinical team has vast experience and competence in managing side effects and adverse events related to medication use in these patients. Where adverse events related to medication use cannot be managed in the home, the patients will be admitted to hospital at Mount Sinai. Generally, this medical care will

be billed to the research subject and/or his/her health care insurance in the ordinary manner and the research subject will be responsible for all treatment costs not covered by insurance, including deductibles, co-payments and coinsurance. This does not prevent the research subject from seeking payment for injury related to malpractice or negligence. As outlined above, interviews can arouse emotions in patients and caregivers. We have outlined the provisions for this eventuality above.

### **Expected Direct Benefit to Subjects**

The study is anticipated to have a number of benefits for subjects (patients and caregivers) in both intervention and control arms.

#### **1. Intervention subjects**

Patients and caregivers in the intervention arm will benefit from receiving an additional in-home care program delivered through video visits and telephone by highly trained and skilled professionals, and designed to address their needs. It is hoped that the intervention will bring about reduction in patients' symptom burden and improvement in quality of life, and reduce burdensome hospitalizations. Additionally, it is hoped that the intervention will lead to reduction in caregiver burden, and improvement in overall caregiver satisfaction. Subjects will receive the benefit of participating in a research study, which is a cited as a highly valued opportunity for patients with end-stage illness and their caregivers.

#### **2. Control subjects**

While control subjects will not receive clinical care, research coordinators will undertake interviews with patients (or proxies) and caregivers at baseline. The results of these interviews will be relayed to the patient's nominated physician. These will serve to highlight previously unrecognized problems. Additionally, caregivers in the control arm will be offered coaching from a health coach on health improvement (e.g., dietary education, smoking cessation). The health coach will be certified in providing health education.

### **Benefit to Society**

There is an urgent imperative to develop in-home models of palliative care to address the significant needs of patients with advanced dementia and their caregivers. In the context of COVID-19 these are being delivered increasingly through the use of telemedicine. Such models of care must be scalable and deliverable in the context of limited numbers of specialist trained providers. This study, and the program of research it advances, will be of great benefit to the wider population of patients with dementia and their caregivers through the development and evaluation of an innovative new care model mapped to their needs.

### **Provisions to Protect the Privacy Interests of Subjects**

#### **1. Recruitment**

Patients will be recruited through a member of their Mount Sinai healthcare team. The research team will contact the patient and their caregiver only after they have demonstrated interest in the study.

#### **2. Enrollment**

The consent forms will be emailed to the patient's proxy (in the event that they lack capacity to consent) and the baseline interview for both the patient/ informant and caregiver will be conducted via telephone. The research team will ensure the subject has understood all the information in the consent forms.

#### **3. Privacy protections during the study**

At the time of enrollment all subjects will be informed that information arising in the course of clinical care will be recorded in the patient's electronic medical record, which can be viewed by the clinical team and other providers within the Mount Sinai Health System as necessary to provide clinical care. Clinical information will not be shared with providers not involved in the patient or caregiver's care without their prior consent. Information arising from interviews will only be shared with the subject's provider with their consent, unless in the case that they are considered to be at risk to themselves or otherwise mandated by law.

### **Economic Impact on Subjects**

We do not anticipate that subjects will incur any economic costs through participation in the research study. Subjects will not be charged for their care or participation in this study.

**11. Subjects - Adults Without Capacity**

There is Anticipated Direct Benefit Yes  
to the Subjects

Assent is Required of All Subjects Capable of Being Consulted

***Select Which of the Following Best Describes the Risk to Subjects***

*\* Intervention: the risk to the subjects is presented by an intervention or procedure that holds out the prospect of direct benefit for the individual subject.*

*\* Monitoring Procedure: more than minimal risk to subjects is presented by a monitoring procedure that is likely to contribute to the subject's well-being.*

Risk to Subjects Intervention

